Statistical Method:	
General Statistical Methodology
 
All statistical processing will be performed using SAS® version 9.3 or later unless otherwise stated. Data will be summarized using descriptive statistics. No inferential testing or imputations for missing data will be performed. No interim analyses are planned for the co-primary variables. For categorical parameters, the number and percentage of patients in each category will be presented. For continuous parameters, descriptive statistics will include n (number of patients), mean, standard deviation, median, minimum and maximum.
 
Populations Analyzed
 
All analyses will be performed using the Safety Population of the study. Part of this population will be referred as the extension safety population, and part as a new enrolled safety population. All patients who receive at least one confirmed dose of S5G4T-1 (in either Study SGT-54-01 or Study SGT-54-02, and in this study or for new patients in this study) and have at least one assessment will be included in the Safety Population.
 
The number of patients included in the Safety Population will be summarized.
 
Analysis of Efficacy
 
This study is not intended to assess efficacy, but rather the IGA is included to determine the need for treatment and subsequent re-treatment. after the initial 12-week treatment course (in either Study SGT-54-01 or Study SGT-54-02 or for those patients not previously enrolled in Study SGT-54-01 or Study SGT-54-02) and any subsequent 4-week courses, if applicable. Certain efficacy data and endpoints will, however, be summarized.
 
Descriptive statistics will be used to summarize the assessment of efficacy. IGA scores will be summarized at Baseline Visit of Study SGT-54-01 or Study SGT-54-02 or at the Screening visit of SGT-54-07 for those patients not previously enrolled in Study SGT-54-01 or Study SGT-54-02, and entry into the study (SGT-54-07) and every 4 weeks through end of the study. The number and percentage of patients who achieve treatment success at the scheduled study visits will be tabulated. A patient will be considered a success if their IGA score is clear or almost clear.
 
Rosacea Quality of Life Questionnaire (RosaQoL) will be completed at Baseline, Visits 5, 8, 11, 14 and End of Study visits. The RosaQoL data of patients who were enrolled from SGT-54-01 or SGT-54-02, will be used from the questionnaire completed at Visit 6/Week 12 of SGT-54-01 or SGT-54-02.

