14. CLINICAL OUTCOME ASSESSMENTS

14.1. Investigator Global Assessment (IGA)

The IGA will be performed at all study visits.

If a patient is assessed as “clear” (0) or “almost clear” (1), the patient will not be dispensed the study product. If a patient is assessed as “mild”, “moderate” or “severe” (2, 3 or 4, respectively), study product will be dispensed and the patient will use the study product daily according to patient instructions.

In the event a subject is not dispensed IP at a given visit due to an IGA of "clear" or "almost clear," and the subject's rosacea condition worsens, an unscheduled visit can be performed for assessing the subject and dispensing IP, if appropriate.

The IGA scale provided in [Table 1](#) will be used to describe the severity grade and subsequent score:

Table 1: Investigator Global Assessment (IGA) Scale

Grade	Description
0 – Clear	Skin clear of inflammatory papules or pustules
1 – Almost Clear	Very few small papules or pustules and very mild dull erythema is present
2 – Mild	Few small papules or pustules and mild dull or light pink erythema is present
3 – Moderate	Several to many small or larger papules or pustules and moderate light to bright red erythema is present
4 – Severe	Numerous small and/or larger papules or pustules and severe erythema that is bright red to deep red is present

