8. STATISTICAL AND ANALYTICAL PLANS

8.1 General Methodology

All statistical processing will be performed using SAS® version 9.4 or later unless otherwise stated.

Descriptive statistics will be used to provide an overview of the efficacy and safety results. For categorical parameters, the number and percentage of subjects in each category will be presented. For continuous parameters, descriptive statistics will include n (number of subjects), mean, standard deviation (SD), median, minimum (min) and maximum (max).

No inferential testing or imputations for missing data will be performed. No interim analyses are planned.

All analyses will be performed using the Safety Population of the study.

Where applicable the analysis will be presented by overall treatment group in 54-07 as well as by treatment group assignment in 54-01/54-02.

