8.8.2 Retreatments

The number of retreatments is defined as the number of clinical confirmations of the condition for which the subject was initially treated after the first treatment period with S5G4T-1. For rollover subjects previously treated with vehicle, this is the number of treatments after the initial treatment in 54-07. For rollover subjects previously treated with S5G4T-1, this is the number of treatments in 54-07 following the cessation of the treatment which began in 54-01 or 54-02. A clinical confirmation of the condition will be defined as IGA no longer being clear or almost clear after a previous IGA of clear or almost clear. When a subject has a clear or almost clear IGA in 54-07, it is expected they were instructed not to dose until the IGA reached mild, moderate or severe.

The number of treatment free days until the first retreatment (relapse) will be calculated and summarized. Relapse will be defined as a subject no longer having an IGA of clear or almost clear after a previous visit IGA of clear or almost clear. When a subject has a clear or almost clear IGA in 54-07, it is expected they were instructed not to dose until the IGA reached mild, moderate or severe. Number of treatment free days until first retreatment is defined as the number of days between an initial IGA assessment of clear or almost clear while the subject was receiving S5G4T-1 until an IGA of mild, moderate or severe.

For rollover subjects previously treated with vehicle, the number of treatment free days will be the number of days between the end of their first treatment of S5G4T-1 in 54-07 (when the subject has an IGA of clear or almost clear) and the start of the next treatment in 54-07 (when the

subject has an IGA indicating they should dose) if they treated with S5G4T-1 again or the end of the subject's participation in 54-07. For rollover subjects previously treated with S5G4T-1, the number of treatment free days will be the number of days between the end of the treatment that began in 54-01 or 54-02 (when the subject has an IGA of clear or almost clear) and the start of the next treatment in 54-07 (when the subject has an IGA indicating they should dose) if they treated with S5G4T-1 again or the end of the subject's participation in the 54-07.

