Descriptive statistics for time to relapse (number of treatment free days until retreatment) and number of retreatments will be presented. A confidence interval (CI) for the median time to relapse will be presented using the Kaplan–Meier method. Patients who discontinue in 54-07 while not being treated and had not yet previously relapsed will be considered censored in the Kaplan–Meier analysis.

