3 - Severe	xx (xx.x%)	xx (xx.x%)	xx (xx.x%)
Week 44^b			
n	xx	NA	xx
0 - None	xx (xx.x%)		xx (xx.x%)
1 - Mild	xx (xx.x%)		xx (xx.x%)
2 - Moderate	xx (xx.x%)		xx (xx.x%)
3 - Severe	xx (xx.x%)		xx (xx.x%)

^a Baseline is defined as the baseline value from SGT-54-01/SGT-54-02.

^b Table summaries based analysis visits, representing time from first dose of E-BPO 5% Cream.

SOURCE: USERNAME\SPONSOR\PROJECT\JOBNAME (DATE,TIME)

Table 14.2.4: Summary of Telangiectasia Assessment at Each Evaluation
(Safety Population)
(Page 5 of 5)

Telangiectasia Assessment	SGT-54-01/SGT-54-02 Vehicle Cream (N=xxx)	SGT-54-01/SG-54-02 E-BPO 5% Cream (N=xxx)	SGT-54-07 E-BPO 5% Cream (N=xxx)
Week 48 ^b			
n	xx	NA	xx
0 - None	xx (xx.x%)		xx (xx.x%)
1 - Mild	xx (xx.x%)		xx (xx.x%)
2 - Moderate	xx (xx.x%)		xx (xx.x%)
3 - Severe	xx (xx.x%)		xx (xx.x%)
Week 52 ^b			
n	xx	NA	xx
0 - None	xx (xx.x%)		xx (xx.x%)
1 - Mild	xx (xx.x%)		xx (xx.x%)
2 - Moderate	xx (xx.x%)		xx (xx.x%)
3 - Severe	xx (xx.x%)		xx (xx.x%)

^a Baseline is defined as the baseline value from SGT-54-01/SGT-54-02.

^b Table summaries based analysis visits, representing time from first dose of E-BPO 5% Cream.

SOURCE: USERNAME\SPONSOR\PROJECT\JOBNAME (DATE,TIME)

Table 14.2.5: Summary of Reoccurrence
(Safety Population)

	E-BPO 5% Cream (N=xxx)
Number of Retreatments	
n	xx
Mean	xx.x
SD	xx.xx
Median	xx.x
Min. to Max.	xx to xx
Number of Treatment Free Days Until First Retreatment	
n	xx
Median ^c (days)	xx.x
95% Confidence Interval ^c	(xx.x, xx.x)

^a Number of retreatments is defined as the number of times a subject's IGA goes from clear or almost clear to mild, moderate or severe after the subject was clear or almost clear while receiving E-BPO 5% Cream.

^b Number of treatment free days until first retreatment is defined as the number of days between an initial IGA assessment of clear or almost clear while the subject was receiving E-BPO 5% Cream until an IGA of mild, moderate or severe.

^c Median and 95% confidence intervals based on Kaplan-Meier method.

SOURCE: USERNAME\SPONSOR\PROJECT\JOBNAME (DATE,TIME)

Table 14.3.0.1: Summary of Extent of Exposure
(Safety Population)
(Page 1 of 2)

	SGT-54-01/SGT-54-02 Vehicle Cream (N=xxx)	SGT-54-01/SG-54-02 E-BPO 5% Cream (N=xxx)	SGT-54-07 E-BPO 5% Cream (N=xxx)
Total Number of Days of Exposure			
n	xx	xx	xx
Mean	xx.x	xx.x	xx.x
SD	xx.xx	xx.xx	xx.xx
Median	xx.x	xx.x	xx.x
Min. to Max.	xx to xx	xx to xx	xx to xx
Total Number of Applications			
n	xx	xx	xx
Mean	xx.x	xx.x	xx.x

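### Table 14.2.5 pools two rollover cohorts with different first S5G4T-1 courses into one median time to relapse; the median should also be shown by prior treatment

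*SAP*

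**What the plan says.** SAP 8.8.2 defines the treatment-free interval separately by what the patient received in 54-01/54-02. For prior vehicle patients the clock starts at the "end of their first treatment of S5G4T-1 in 54-07 (when the subject has an IGA of clear or almost clear"). For prior S5G4T-1 patients it starts at the end of the course that began in the parent trial. Of the Kaplan-Meier analysis the same section says "A confidence interval (CI) for the median time to relapse will be presented"; it mentions no split by cohort. SAP 8.1.11 declares subgroups not applicable.

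The Table 14.2.5 shell has one column. Its row "Number of Treatment Free Days Until First Retreatment" holds one median and one 95% CI. Footnote b to the table, and one sentence of 8.8.2, give another clock start: the initial clear or almost clear IGA while the patient was receiving the cream.

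The general rule in SAP 8.1 is that, where applicable, results are shown for 54-07 overall "as well as by treatment group assignment in 54-01/54-02". The other efficacy shells (14.2.1.1 to 14.2.4) have three columns: prior vehicle, prior S5G4T-1 and 54-07 total.

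The end of a course in 54-07 follows from Protocol 14.1: at IGA 0 or 1, "the patient will not be dispensed the study product". SAP 10 confirms that no new patients were enrolled, so the pooled column consists entirely of the two rollover cohorts.

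**The concern.** A median time to relapse is read as a property of the treatment: how long remission lasts once the cream is stopped. Here the first course that precedes the interval is not the same in the two cohorts. One has had about 12 weeks or more of S5G4T-1. The other may have had as little as about 4 weeks, ended by the first good IGA.

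If duration of remission differs between these situations, one pooled median describes neither. It would also move with the cohort proportions, which reflect parent-trial allocation and who reached clearance as well as the drug. A reader of Table 14.2.5 could not tell which course the median follows.

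**Working it through.** The plan states no relapse rate, cohort count or expected median, so there is no figure to reproduce. What can be checked is the course length and, under stated assumptions, how a pooled median behaves.

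**1. Length of the first course, from the visit schedule (days after Day 1)**

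- Prior S5G4T-1: Protocol 12.1 and SAP 6.1 require completion of 12 weeks ±4 days in the parent trial. Nominal 85 − 1 = 84 days; earliest 81 − 1 = 80 days. A patient at IGA 2 or more at 54-07 entry is dispensed product and continues at least to the next scheduled IGA, nominally 84 + 28 = 112 days.
- Prior vehicle: the first scheduled IGA after 54-07 Baseline is Week 4, Day 29 ±10 (SAP 6.1). Nominal 29 − 1 = 28 days; earliest 19 − 1 = 18 days. An unscheduled visit could be earlier.

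The nominal minima are therefore 84 and 28 days. The ranges overlap above 84 days, because a prior vehicle patient who clears late may also have a long course.

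**2. Maximum off-treatment follow-up**

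- Prior S5G4T-1, clear at 54-07 entry: 281 − 1 = 280 days.
- Prior vehicle, clear at Week 4: 281 − 29 = 252 days.

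This is a difference in censoring, which Kaplan-Meier accommodates. It is not counted as a defect.

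**3. Pooled median under assumed exponential relapse**

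Let *w* be the S5G4T-1 share, *a* the assumed prior S5G4T-1 median and *b* the assumed prior vehicle median. The pooled median *t* solves

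w·2^(−t/a) + (1 − w)·2^(−t/b) = 0.5

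With a = 120 and b = 56:

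- w = 0.50, t = 80.2: 0.50 × 0.629 + 0.50 × 0.371 = 0.500
- w = 0.67, t = 91.9: 0.67 × 0.588 + 0.33 × 0.321 = 0.500

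| Assumed medians, prior S5G4T-1 / prior vehicle (days) | w = 0.50 | w = 0.67 | Shift |
|---|---|---|---|
| 120 / 56 | 80.2 | 91.9 | +11.7 |
| 168 / 56 | 92.6 | 113.7 | +21.1 |
| 84 / 84 | 84.0 | 84.0 | 0 |
| 56 / 112 | 77.8 | 69.1 | −8.7 |

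The third row shows no dependence on mix when the medians agree; the fourth shows the direction reversing.

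**4. Allowing for visits about every 28 days**

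Relapse is seen only at visits, so the reported median moves in steps. A Kaplan-Meier simulation used 400 patients, 28-day visits, and censoring at 252 days (prior vehicle) or 280 days (prior S5G4T-1). With assumed medians of 42 days (vehicle) and 112 days (S5G4T-1), the typical pooled median was 112, 84 and 56 days at vehicle shares of 25%, 50% and 75%. With 84 days in both cohorts it stayed at 84. A modest difference can also be hidden by the visit grid: with exponential medians of 56 (vehicle) and 84 (S5G4T-1), the first visit at which half have relapsed is day 84 at every vehicle share tried from 10% to 90%.

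**5. The conflicting clock start**

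Under footnote b, a prior S5G4T-1 patient first clear at parent Week 4 would start the clock there, while still on a 12-week course. Up to 84 − 28 = 56 days on treatment would then count as treatment-free. Under the end-of-treatment wording in 8.8.2 they would not. For a prior vehicle patient in 54-07 the two definitions largely coincide, because clearance is also when product is withheld. The conflict therefore falls mainly on one cohort.

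**The case against.** The strongest reply is that this is a descriptive summary in a study not intended to assess efficacy, with no inferential testing, and that SAP 8.1 already allows the split where applicable. Several other shells (medical history, concomitant medication, overall adverse events, vital signs) also use one column. The first part stands and limits the weight of the point. The rest does not remove it: Table 14.2.5 is the only efficacy shell without the split, although its endpoint is the one defined cohort by cohort.

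Four stronger readings are tempting, and the documents do not support them.

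- *The pooled median certainly shifts with cohort mix.* It does so only if the relapse curves differ around the median, and nothing in the documents establishes that. Every relapse figure above is assumed.
- *The protocol promises remission after a 12-week course.* The synopsis phrase "after the initial 12-week treatment course" concerns using IGA to decide on re-treatment. It does not define relapse. Protocol 18.3 and SAP 7.1 omit the 12 weeks, and no objective names that target.
- *The prior S5G4T-1 column alone would give remission after a 12-week course.* It would not. Patients not clear at 54-07 entry continue, so the column follows a course of at least about 12 weeks.
- *The trial cannot answer the question at all.* Listings of IGA, dosing and prior treatment are planned, so the data exist. Only the summary is lacking.

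**Conclusion.** The point holds as a presentation gap in a descriptive endpoint. By design, the single column combines a first course of nominally at least 84 days (80 with the window) with one that can be as short as 28 days (18 with the window). Whether this changes the median, by how much and in which direction cannot be derived from the documents. In the continuous-time illustration, raising the S5G4T-1 share from 50% to 67% moves the pooled median by anything from −9 to +21 days, including zero, depending on the assumed cohort medians and exponential relapse.

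The two clock definitions are a separate inconsistency that splitting the column would not resolve. No test, and no part of the safety objective, is affected.

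**What to change.** In SAP 8.8.2 and Table 14.2.5, apply SAP 8.1 and use the prior vehicle, prior S5G4T-1 and total columns of the other efficacy shells. In each column give the number of retreatments and the Kaplan-Meier median with its 95% CI. Add a row for the length of the first S5G4T-1 course, so that the spread within each cohort is visible. Label the prior S5G4T-1 column as following a course of at least about 12 weeks.

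In the same edit, reconcile footnote b and the matching sentence of 8.8.2 with the end-of-treatment start, so that one clock start applies in text and table.

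The cost is one shell change and a by-cohort run. Prior treatment is already planned for Listing 16.1.7, no new data are needed, and SAP 2 allows updates before database lock. The per-cohort intervals will be wider than the pooled one; the total column can stay.

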18.3. Analysis of Efficacy

This study is not intended to assess efficacy, but rather the IGA is included to determine the need for treatment and subsequent re-treatment after treatment course (in either Study SGT-54-01 or Study SGT-54-02 or for new patients not previously enrolled in Study SGT-54-01 or Study SGT-54-02) and any subsequent 4-week courses, if applicable. Certain efficacy data and endpoints will, however, be summarized.

Descriptive statistics will be used to summarize the assessment of efficacy. IGA scores will be summarized at Baseline Visit of Study SGT-54-01 or Study SGT-54-02 or at the Screening visit of SGT-54-07 for those patients not previously enrolled in Study SGT-54-01 or Study SGT-54-02, and entry into the study (SGT-54-07) and every 4 weeks through end of the study. The number and percentage of patients who achieve treatment success at the scheduled study visits will be tabulated.

The number of retreatments is defined as the number of clinical confirmations of the condition for which the subject was initially treated after the first treatment period with S5G4T-1. For rollover subjects previously treated with Vehicle Cream, this is the number after the initial treatment in Study SGT-54-07. For rollover subjects previously treated with S5G4T-1, this is the number of treatments in Study SGT-54-07 following the cessation of the treatment which began in Study SGT-54-01 or Study SGT-54-02.

The number of treatment free days until the first retreatment (relapse) will be calculated and analyzed. For rollover subjects previously treated with Vehicle Cream, the number of treatment free days will be the number of days between the end of the initial treatment in study SGT-54-07 and the start of the next treatment in study SGT-54-07 if one should be needed or the end of the subject's participation in study SGT-54-07. For rollover subjects previously treated with S5G4T1, the number of treatment free days will be the of days between the end of the initial treatment that began in Study SGT-54-01 or Study SGT-54-02 and the start of the next treatment in study SGT-54-07 if one should be needed or the end of the subject's participation in the study SGT-54-07.

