8.1.3 Visit Windowing

For subjects receiving S5G4T-1 in 54-01/54-02, data from 54-01/54-02 will be included in summaries of 54-07. For subjects receiving vehicle in 54-01/54-02, baseline values will be sourced from 54-01/54-02 and data from follow-up visits of 54-07 will be used in summaries. The table below details the analysis visits to be summarized and the associated visits from 54-01/54-02 or 54-07 which will be sourced for each type of subject.

Analysis Visits for Efficacy and Safety Assessments

Analysis Visit	Subjects Receiving S5G4T-1 in 54-01/54-02	Subjects Receiving vehicle in 54-01/54-02
Week 4	54-01/02 - Week 4	54-07 - Week 4
Week 8	54-01/02 - Week 8	54-07 - Week 8
Week 12	54-01/02 - Week 12	54-07 - Week 12
Week 16	54-07 - Week 4	54-07 - Week 16
Week 20	54-07 - Week 8	54-07 - Week 20
Week 24	54-07 - Week 12	54-07 - Week 24
Week 28	54-07 - Week 16	54-07 - Week 28
Week 32	54-07 - Week 20	54-07 - Week 32
Week 36	54-07 - Week 24	54-07 - Week 36
Week 40	54-07 - Week 28	54-07 - Week 40
Week 44	54-07 - Week 32	Not available
Week 48	54-07 - Week 36	Not available
Week 52	54-07 - Week 40	Not available

Data from 54-07 will be mapped to the appropriate analysis visit described above based on nominal visit indications. Data from Early Termination (ET) and unscheduled visits will be determined using analysis visit windows. The analysis visit windows for ET and unscheduled visits are presented in the following table.

SGT-54-07 Analysis Visit Windows for Efficacy and Safety Assessments

Nominal Visit	Target Study Day¹	Window (Days)
Week 4	29	22 to 42
Week 8	57	43 to 70
Week 12	85	71 to 98
Week 16	113	99 to 126
Week 20	141	127 to 154
Week 24	169	155 to 182
Week 28	197	183 to 210
Week 32	225	211 to 238
Week 36	253	239 to 266
Week 40	281	267 to 294
Week 44	309	295 to 322
Week 48	337	323 to 350
Week 52	365	351 to 378

¹ Number of days since nominal Baseline visit of 54-07

Data collected at ET and unscheduled visits prior to study day 22 will not be analyzed. Data collected at ET and unscheduled visits after study day 378 will not be included in analyses.

The definition for the study day included in each study window is defined as below:

Study Day prior to Day 1 = Visit Date – Day 1 Date

Study Day on or after Day 1 = Visit Date – Day 1 Date + 1

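### Table 14.2.5 footnote a omits the limits SAP 8.8.2 puts on the retreatment count, so for prior-S5G4T-1 rollovers an IGA change during parent-trial dosing can be counted as a retreatment

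*SAP*

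**What the plan says.** SAP 8.8.2 sets out the count in layers. The general rule counts "clinical confirmations of the condition for which the subject was initially treated after the first treatment period with S5G4T-1". It is then made specific by cohort. For patients who had S5G4T-1 in the parent trial, "this is the number of treatments in 54-07 following the cessation of the treatment which began in 54-01 or 54-02". For patients who had vehicle, it is the number of treatments after their first course in 54-07. Protocol 18.3 gives the same rule for the first group: "For rollover subjects previously treated with S5G4T-1, this is the number of treatments in Study SGT-54-07 following the cessation of the treatment". Within these limits, 8.8.2 says how a recurrence is recognised: "A clinical confirmation of the condition will be defined as IGA no longer being clear or almost clear after a previous IGA" of 0 or 1.

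The shell for Table 14.2.5 carries its own definition in footnote a: "Number of retreatments is defined as the number of times a subject's IGA goes from clear or almost clear to mild, moderate or severe", followed by one qualifier, "after the subject was clear or almost clear while receiving E-BPO 5% Cream". It says nothing about which study the change must occur in, or about a course having ended first.

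SAP 8.1.3 states: "For subjects receiving S5G4T-1 in 54-01/54-02, data from 54-01/54-02 will be included in summaries of 54-07". Its mapping table takes analysis Weeks 4, 8 and 12 for this cohort from 54-01/54-02. For prior-vehicle patients only the baseline values come from the parent trial.

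**The concern.** A retreatment is meant to be a new course after an earlier one has stopped. SAP 8.8.2 describes stopping at IGA 0/1 as something expected in 54-07; it says nothing of the kind about the parent trials. A prior-S5G4T-1 patient who is almost clear at parent Week 4 and mild at parent Week 8 has therefore most likely just fluctuated while still applying the product. Footnote a, taken literally, calls that a retreatment; SAP 8.8.2 does not.

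A programmer working from the shell could produce one count, and a programmer working from the text another. The footnote would be printed beneath the result as its definition. Table 14.2.5 has a single pooled column, so a reader could not see that the extra counts come from one cohort only, or that the pooled figure shifts with the cohort mix.

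**Working it through.** The documents give no figure for the retreatment count, so there is nothing to reproduce. The check compares the two rules and applies both to the same visit records.

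**1. The rules side by side, for a prior-S5G4T-1 patient**

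| Element | Footnote a | SAP 8.8.2 and Protocol 18.3 |
|---|---|---|
| Event | IGA 0/1 to 2+ | Treatment for a recurrence, recognised by IGA 0/1 to 2+ |
| Study | Not restricted | 54-07 only |
| Timing | After a 0/1 rating on E-BPO | After the course begun in the parent trial has ended |

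The footnote's qualifier removes changes that follow a clear rating on vehicle. It does not remove parent-trial changes in this cohort, because these patients were on E-BPO at the time.

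**2. Is parent dosing continuous?** Three places point that way. Protocol section 11 describes 12 weeks of treatment in the parent trials. SAP 8.8.2 confines the expected stop at IGA 0/1 to 54-07. The shell for Listing 16.2.5.3 shows one first-to-last-dose interval plus deviations for 54-01, against several dosing intervals for 54-07. This remains an inference.

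**3. Two patients.** Parent Week 12 is also the 54-07 Baseline, the first visit at which the IGA-based dispensing rule applies. The 8.8.2 count therefore runs from that visit onward, and the footnote count over the whole sequence.

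- Patient A: parent Weeks 4/8/12 = 1/2/2, then IGA 2 at all ten 54-07 visits. Footnote a: 1 (Week 4 to 8). SAP 8.8.2: 0, because no course ended.
- Patient B: parent Weeks 4/8/12 = 2/1/2; in 54-07, Week 4 = 2, Weeks 8 and 12 = 1, Week 16 = 2, and 2 thereafter. Footnote a: 2 (parent Week 8 to 12, and 54-07 Week 12 to 16). SAP 8.8.2: 1.

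**4. All patterns.** Write C for IGA 0/1 and N for 2+. Three parent visits give 2 × 2 × 2 = 8 patterns. Whatever follows in 54-07, the difference (footnote a minus 8.8.2) is:

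- +1 for CNN, CNC, CCN and NCN (4 patterns);
- 0 for NNN, NNC, NCC and CCC (4 patterns).

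The difference cannot exceed 1, because two C-to-N changes need four visits. If a fourth parent visit were used, CNCN would give +2 and no other pattern more than +1. SAP 8.1.3 maps only three. These are possible patterns, not equally likely ones, so 4 of 8 is not a rate.

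For prior-vehicle patients the difference from this source is 0: no follow-up visits come from the parent trial, and the footnote requires the clear rating to be on E-BPO.

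**5. Effect on the pooled mean.** Let f be the share of the table N who are prior-S5G4T-1 patients and q the proportion of those with a C-to-N change within parent Weeks 4 to 12. The overstatement is f × q × 1. The documents give neither input; both are assumed.

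| f | q = 2% | q = 5% | q = 10% | q = 15% |
|---|---|---|---|---|
| 0.50 | 0.010 | 0.025 | 0.050 | 0.075 |
| 0.667 | 0.013 | 0.033 | 0.067 | 0.100 |

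The shell prints the mean to one decimal, so the largest shift here is about one printed unit.

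**The case against.** The strongest reply is that the SAP text already has the right rule, the protocol agrees with it, and the footnote is shorthand that any competent programmer would read with 8.8.2. It is also fair that parent IGAs are not expressly assigned to this table. The analysis-visit mapping in 8.1.3 serves by-visit summaries, and those shells carry a note saying so; Table 14.2.5 has no such note.

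Part of this stands. The rule in 8.8.2 is correct, and the use of parent visits in this table is an inference from the broad wording of 8.1.3. But the footnote is worded as a definition, not a cross-reference. SAP section 2 ranks the SAP above the protocol, and nothing ranks the SAP text above its own shells.

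Three stronger readings are tempting, and the documents do not support them:

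- A reader might infer that the footnote counts every IGA change from 0/1 to 2+. It does not: its second half requires a clear or almost clear rating on E-BPO, which excludes changes on vehicle.
- A reader might infer that 8.8.2 contradicts itself, because its recurrence sentence also rests on an IGA change. That sentence defines a term used inside the two limits and does not compete with them.
- A reader might infer that the count should depend on whether product was withheld. The SAP deliberately works from IGA and says only that non-dosing is expected. Such a rule would change the variable and blur the separate rule for prior-vehicle patients.

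**Conclusion.** The point holds as a wording conflict with a real but small numerical consequence. Footnote a leaves out both limits that SAP 8.8.2 and Protocol 18.3 place on the count for prior-S5G4T-1 patients, and the two definitions give different numbers for the same patient.

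That the definitions differ needs no assumed rates. That the difference reaches the reported table rests on two inferences: uninterrupted parent dosing, and parent IGAs entering this table through 8.1.3. The range of about 0.01 to 0.10 for the pooled mean rests in addition on the assumed values of f and q. The median may not move, since few patients are affected and each by a single count.

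The documents do not support reading this as a threat to the study's conclusions. The table is descriptive, no inferential testing is planned, the study is stated not to assess efficacy, and the retreatment count is not among the safety endpoints. It is worth correcting before database lock because the repair is cheap and the printed definition would otherwise be wrong.

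**What to change.** Add to footnote a of Table 14.2.5 wording to this effect:

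*For subjects who received E-BPO in 54-01/54-02, only transitions in 54-07 that follow the end of the course begun in the parent trial are counted; IGA changes during 54-01/54-02 are not. For subjects who received vehicle, only transitions after the initial 54-07 treatment are counted (Section 8.8.2).*

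It would help to say that a change from parent Week 8 to parent Week 12 belongs to the parent trial, because Week 12 is also the 54-07 Baseline visit. Keep the two cohort rules in 8.8.2 and the IGA-based recognition of recurrence, and add one sentence there saying that it applies within those cohort limits.

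The cost is SAP and shell wording only, with no change to data collection or to any clinical procedure. The downside is that the reported mean number of retreatments becomes slightly smaller.
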